Appendix A

Section 2: Oral Hygiene Practices

The question	Responses	Old codes	New scores
B.1 – Do you brush your teeth?	Yes	1	1
	No.	2	0
B1.1 How often do you usually brush your teeth?	Once a day	1	1
	Twice a day or more	2	2
	Sometimes	3	3
B.1.3 - How long do you spend brushing your teeth?	A minute or less	1	1
	Two minutes	2	2
	More than two minutes	3	3
B.1.4 - How do you brush your teeth?	Bass method	1	2
	Scrubbing method	2	1
	Modified Bass method	3	3
	Other	4	0
B.1.5 - What kind of bristles does your toothbrush have?	Soft bristles	1	2
	Medium bristles	2	3
	Hard bristles	3	1
	I am not sure	4	0
B.1.6 - How often do you change your toothbrush?	Every month	1	3
	Every two months	2	2
	Every three months	3	1
	Other	4	0
B.1.7 - Do you use other oral and dental cleaning tools besides the toothbrush?	Dental floss	1	3
	Interdental brush	2	2
	Mouthwash	3	1
	Do not use	4	0
B.1.8 - Do you visit the dentist in your life?	Yes.	1	1
	No.	2	0
B.1.9- How did you visit the dentist?	Regularly	1	3
	Sometime	2	2
	Pain	3	1
	Before 6 months	1	3
	Before 6-12 months	2	2

B.1.10 - When was the last time you visited the dentist?	Before 1-2 years	3	1
	Before 3-5 years	4	0
B.1.11 - If you visited the dentist, what was the purpose of your visit?	Pain	1	0
	Recommendation from a friend or relative	2	1
	Recommendation from another dentist	3	2
	Routine dental check-up	4	3
	Teeth and gum cleaning	5	4

Section 3: Diet Habits

C.1.1 - Do you eat breakfast on weekdays?	Never	1	0
	Once a week	2	1
	Twice a week	3	2
	Three times a week	4	3
	Four times a week	5	4
	Every day	6	5
C.2.1-Do you have breakfast on weekends?	Never	1	0
	Once a week	2	1
	Every weekend	3	2

C.2 - How often do you eat or drink the following items? (Tick one box for each item by marking an "X" under the option that applies to you in each row):

Item	Never	Less than once a week	Once a week	2-4 times a week	6 times a week	Once a day	More than once a day
Fruits	0	1	2	3	4	5	6
New code	0	1	2	3	4	5	6
Vegetables	0	1	2	3	4	5	6
New code	0	1	2	3	4	5	6
Sweets (e.g., candy or chocolate)	0	1	2	3	4	5	6
New code	6	5	4	3	2	1	0
Soft drinks or any sugar-containing beverages	0	1	2	3	4	5	6
New code	6	5	4	3	2	1	0
Milk and dairy products	0	1	2	3	4	5	6

New code	0	1	2	3	4	5	6
Red meat	0	1	2	3	4	5	6
New code	0	1	2	3	4	5	6
Fish	0	1	2	3	4	5	6
New code	0	1	2	3	4	5	6
Water	0	1	2	3	4	5	6
New code	0	1	2	3	4	5	6
Nuts	0	1	2	3	4	5	6
New code	0	1	2	3	4	5	6
Pastries	0	1	2	3	4	5	6
New code	6	5	4	3	2	1	0

Section 4: Smoking behaviours

The question	Responses	Old codes	New scores
D.1- Do you currently smoke (at least one cigarette)?	Yes	1	2
	No	2	0
D.2 - How frequently do you smoke cigarettes or use other tobacco products?	Every day	1	1
	At least once a week but not every day	2	2
	Less than once a week	3	3
	I don't smoke	4	4
D.2.2 - If you smoke cigarettes, how many cigarettes do you usually smoke per week?	26 and over		0
	21-25 cigarettes		1
	16-20cigarettes		2
	11-15cigarettes		3
	6-10cigarettes		4
	0-5cigarettes		5
D.3 - Have you ever smoked a waterpipe (hookah)?	Yes	1	2
	No	2	0
D.4 - How often do you currently smoke a water pipe?	Every day	1	1
	At least once a week but not every day	2	2
	Less than once a week	3	3
	I don't smoke waterpipe	4	4

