## **Secondary Aims**

To assess the effect of the intervention on students' oral hygiene practices, including brushing frequency, technique, and duration.

To evaluate changes in dietary habits following the intervention, particularly regarding breakfast consumption and intake of nutritious foods.

To examine changes in smoking behaviours, including cigarette and waterpipe use, among students exposed to the educational sessions.

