### **Data Collection Processes**

The Al-Quds Committee for Ethical Considerations approved this study (REF.13/24). Consent forms were distributed to students, and their approval was sought before data collection began.

The researcher trained five dentists to conduct interviews and dental examinations, ensuring the data collection process was standardised and calibrated. Training sessions for the data collectors were held every 15 days throughout the research period to maintain consistency and accuracy in data collection.

During the baseline phase, all participants were provided with a comprehensive explanation of the study. Baseline data were collected in March 2024. The selected participants were randomly divided into intervention and control groups, ensuring that both groups were matched by age and gender. The control group received one oral educational session, while the intervention group participated in six sessions. The educational sessions were held every 10 days over two months.

After two months of interactive education, participants were re-examined and interviewed. Follow-up data were collected in the same schools using the same dental examination measures and questionnaires used during the baseline phase.

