Test to use: Paired t-test, as the data is normally distributed.

B. Between-Group Analysis (Post-intervention comparison):

Purpose: To compare the post-intervention CPITN scores between the intervention and control groups.

Test to use: Independent T-test as the data is normally distributed

Note: The two groups were examined for their differences in baseline measurement.

2. Can interactive educational sessions reduce **S-Oral hygiene index scores** among 9th-grade students in Nablus City within two months?

1. Data Type and Variables

Dependent Variable: Simplified Oral Hygiene Index (S-OHI) score → Continuous quantitative variable

Independent Variable: Group type (Intervention vs. Control) → Binary categorical variable

Time Points: Pre-intervention (baseline)

Post-intervention (after two months) → true experimental design

2. Statistical Design

Since there are two time points and two groups, the analysis includes:

A. Within-Group Analysis (Intervention group only):

Purpose: To assess whether there is a significant improvement (reduction) in S-OHI scores after the interactive educational sessions.

Test to use: *Paired t-test*, as the data is normally distributed.

B. Between-Group Analysis (Post-intervention comparison):

Purpose: To compare the post-intervention S-OHI scores between the intervention and control groups.

Test to use: *Independent t-test*, as the data is normally distributed

3. Will oral hygiene practices, smoking habits, and dietary habits improve among 9th-grade students after interactive educational sessions are applied in Nablus City?

Questionnaire responses related to oral hygiene practices, dietary habits, and smoking behaviour were **recoded** into scale variables to facilitate the computation of mean scores pre-and post-intervention. Correct answers reflecting preventive behaviours, in line with American Dental Association (2023) guidelines, were assigned the highest scores, while incorrect responses received the lowest scores, for example:

- "Do you clean your teeth?": Yes = 1, No = 0
- "How often do you clean your teeth?": Once/day = 1, Twice/day = 2, Three times/day = 3
- "How long does it take to clean your teeth?": One minute = 1, Two minutes = 2, More than two minutes = 3, Don't know = 0
- "Brushing technique": Scrubbing = 1, Bass = 2, Modified Bass = 3
- "Toothbrush type": Hard bristle = 1, Soft bristle = 2, Medium bristle = 3

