"Toothbrush replacement frequency": Every three months = 1, Two months = 2, Monthly = 3

Additional coding schemes are provided at the end of this document. The overall mean differences in oral hygiene practices, dietary habits, and smoking behaviour scores were then compared between groups using independent sample t-tests, with sub-analyses conducted for each behavioural domain separately. Statistical significance was set at $p < 0.05$.

1. Data Type and Variables

Dependent Variables (Behavioural Scores):

- **Oral hygiene practices score** → Continuous quantitative
- **Smoking habits score** → Continuous quantitative
- **Dietary habits score** → Continuous quantitative

Independent Variable: Group type (Intervention vs. Control) → Binary categorical

Time Points: Pre-intervention (baseline)

Post-intervention (after two months) → True experiment design (pre-post)

2. Statistical Design

Since the question involves **multiple behaviours** and **two time points**, the analysis will be conducted separately for each behavioural domain:

A. Within-Group Analysis (Intervention Group Only)

- **Purpose:** To evaluate if there was a significant improvement in each behaviour **after the intervention**.
- **Test to use:** Paired t-test for:
 - Oral hygiene practices score

- Dietary habits score
- Smoking habits score

(Assumes normal distribution)

B. Between-Group Analysis (Post-Intervention Comparison)

- **Purpose:** To compare post-intervention behavioural scores between intervention and control groups.
- **Test to use:**
 - **Independent t-test** for:
 - Oral hygiene practices
 - Dietary habits
 - Smoking behavior

(Assumes normal distribution)

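### A lifetime waterpipe item (D.3) scores starting waterpipe use as improvement, and the hygiene score mixes dental attendance (11 of 30 points) with the brushing behaviours named in the aim

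*SAP*

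**What the plan says.** The Protocol (Secondary Aims) sets out to assess oral hygiene practices, "including brushing frequency, technique, and duration". Under Data Collection Processes it states: "After two months of interactive education, participants were re-examined and interviewed", "using the same dental examination measures and questionnaires used during the baseline phase".

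Under its third study question, the SAP recodes questionnaire answers "to facilitate the computation of mean scores pre-and post-intervention". The purpose of the within-group analysis, which is limited to the intervention group, is "To evaluate if there was a significant improvement in each behaviour". The planned t-tests are on three domain scores (hygiene, diet, smoking), and the sub-analyses are by domain. No single item has a planned result, and no item is left out of its score.

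Appendix A, Section 2 puts four dental-visit items in the hygiene score: B.1.8 ("Do you visit the dentist in your life"), B.1.9 (pattern of visits), B.1.10 ("When was the last time you visited the dentist") and B.1.11 (purpose of the visit). Section 4 puts D.3 ("Have you ever smoked a waterpipe (hookah") in the smoking score, with Yes = 2 and No = 0.

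**The concern.** A score meant to show change over two months should be made of items that can change in that time, and that move in the right direction when behaviour improves. D.3 fails on both counts: it cannot register stopping, and it rewards starting.

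The dental-visit items raise a milder problem. They mostly record what happened before the trial and describe attendance rather than cleaning. With more than a third of the hygiene points, they can move the domain score, or hold it still, whatever happens to brushing. A result on the total would then not say whether frequency, technique or duration changed, and the plan has no other analysis that would.

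**Working it through.** The documents state no maximum for either score, so there is no figure to reproduce. All inputs are the new scores in SAP Appendix A.

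**Smoking score**

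Sum of item maxima (D.1, D.2, D.2.2, D.3, D.4): 2 + 4 + 5 + 2 + 4 = 17. D.3 is 2/17 = 11.8%; without it the sum is 15.

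Take a student who had never used a waterpipe at baseline: D.3 = 0, D.4 = 4, subtotal 4. At follow-up:

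- tried it, not using now: 2 + 4 = 6, change +2 (D.4 alone: 0)
- uses less than weekly: 2 + 3 = 5, change +1 (D.4 alone: -1)
- uses weekly but not daily: 2 + 2 = 4, change 0 (D.4 alone: -2)
- uses daily: 2 + 1 = 3, change -1 (D.4 alone: -3)

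D.3 therefore shifts each starter up by 2 points: trying or occasional use registers as improvement, and weekly use as no change. D.2 also asks about other tobacco products. If it moves in step with D.4, the four changes become +2, 0, -2 and -4; the 2-point credit from D.3 is the same. In a post-intervention comparison, a former user (2 + 4 = 6) outscores a student who never used (0 + 4 = 4).

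**Hygiene score**

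Sum of item maxima, B.1 to B.1.11 in order: 1 + 3 + 3 + 3 + 3 + 3 + 3 + 1 + 3 + 3 + 4 = 30. Dental-visit items: 1 + 3 + 3 + 4 = 11. Share: 11/30 = 36.7%; remainder 30 - 11 = 19.

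- If several B.1.7 answers may be added (3 + 2 + 1 = 6): 11/33 = 33.3%.
- If B1.1 is capped at 2: 11/29 = 37.9%.

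The SAP does not say whether items are summed or averaged; with equal item weights the share is the same.

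**What the visit items can do in two months**

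- B.1.8, once Yes, is at its ceiling of 1.
- B.1.9 to B.1.11 (3 + 3 + 4 = 10 points) can rise after a new visit. A student with no earlier visit who attends once for pain gains 1 + 1 + 3 + 0 = 5 points with unchanged brushing, if skipped items count 0 at baseline (an assumption; the SAP is silent). Moving from scrubbing to modified Bass gains 3 - 1 = 2.
- B.1.10 can fall with the calendar. Reading its first category as within the last six months, a visit five months before baseline is seven months old at follow-up, and the score goes from 3 to 2.

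**Coding of brushing frequency**

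The SAP text under the third study question gives the top score of 3 to cleaning three times a day. Appendix A item B1.1 gives 2 to twice a day or more and 3 to the answer Sometimes. The two response lists and scores do not agree, and the Appendix version conflicts with the SAP's rule that preventive answers score highest.

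**The case against.** Four counter-arguments deserve an answer.

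**The visit items are not inert.** A reader might infer that all 11 points cannot improve. The documents do not support that. Only B.1.8, once Yes, is fixed. Protocol Table 2 has session 2 cover professional measures such as scaling and session 3 cover recall intervals, so attendance may be a programme effect. This stands, and it is why the items should be reported separately rather than discarded.

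**No group drift follows.** A reader might infer that B.1.10 pulls the within-group mean down, since with visit dates spread evenly 2/6 = one third of students in the first category would cross its boundary in two months. That count allows no new visits. If visiting continues at a steady rate, new visits offset the ageing of old ones on average, and the group mean does not fall. Even with every student in the top category and no visits at all, the mean loss is 1/3 of a point in 30, or 1.1%. Any drift should also be similar in two concurrent arms. What stands is that an individual student can lose a point through elapsed time alone.

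**No dilution figure follows.** If the visit items carried an assumed 20 to 40% of the score variance, 1 - sqrt(1 - share) would give an 11 to 23% smaller standardised effect. This needs item variances that the documents do not give, no programme effect on visits, and a comparison of post-intervention scores only. The SAP names that comparison but also speaks of comparing mean differences; if those are change scores, stable items largely cancel. The percentage cannot be attributed to this trial.

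**The aim is not a closed list.** It introduces the three brushing behaviours as inclusions, and B.1 to B.1.7 itself holds bristle type, brush replacement and cleaning aids. So including dental visits does not contradict the protocol. It remains true that the three named behaviours have no result of their own. The instrument was also administered in Arabic, so fine points of the English wording should not be pressed.

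None of this rescues D.3.

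**Conclusion.** The point holds for D.3 and, in a limited form, for the hygiene score. D.3 is a lifetime item whose only valid movement adds 2 of 17 points for starting waterpipe use, and D.4 already captures current use. This rests only on Appendix A and on consistent answers from students.

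The hygiene score takes 11 of 30 points (33 to 38% under other readings of B.1.7 and B1.1) from largely historical attendance items, so it mixes attendance with cleaning and leaves frequency, technique and duration without an answer. Separating the two is partly a design choice, because the programme may prompt visits. The size of any effect on the planned tests is not known.

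The issue is minor: these are secondary outcomes, and CPITN and S-OHI are not touched.

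**What to change.** 1. Drop D.3 from the smoking change score and keep D.4. D.1 carries the same Yes = 2, No = 0 coding; dropping D.3 does not cure that, so its direction needs checking too.
2. Reconcile the B1.1 response list and scores between the SAP text and Appendix A before using the item.
3. Then report between-arm results, with confidence intervals, for brushing frequency (B1.1), duration (B.1.3) and technique (B.1.4).
4. Report a brushing and cleaning subscore (B.1 to B.1.7, maximum 19) separately from a dental-attendance subscore (B.1.8 to B.1.11, maximum 11), and state how B.1.9 to B.1.11 are scored for students who have never seen a dentist.
5. Keep the full 30-point score as a sensitivity analysis.

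The cost is recoding and a few extra table rows; no new data are needed. The downside is a shorter hygiene score and a few more secondary comparisons, which should be labelled as such.

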Statistical Analysis Plan (SAP)

Official Title: Effectiveness of an Interactive School-Based Oral Health Education Program in Reducing Periodontal Disease Among Palestinian Adolescents: A Double-Blind Intervention Study

NCT Number:

Document Date: March 1, 2024

Sponsor: Al-Quds University

Overview

This Statistical Analysis Plan outlines the statistical methods and procedures used to analyse data for the intervention study assessing the effect of a school-based oral health education program on periodontal conditions and related behaviours among 9th-grade students in Nablus City, Palestine.

Study Objectives

- Primary: To evaluate the effectiveness of the intervention on CPITN and S-OHI scores.
- Secondary: To assess changes in oral hygiene practices, dietary habits, and smoking behaviours.

Data Preparation and Management

Data were entered into IBM SPSS Statistics version 25.0.

All data were reviewed for completeness and consistency prior to analysis.

Normality testing was conducted using Shapiro-Wilk tests.

Missing data was minimal and handled by complete case analysis.

Statistical Analyses

Descriptive statistics will be used to summarise baseline characteristics by group (mean \pm SD, frequencies, percentages).

- Paired t-tests will be used to assess within-group differences from baseline to post-intervention.
- Independent t-tests were used to compare mean differences between the intervention and control groups.
- Statistical significance was set at $p < 0.05$.
- Confidence intervals were calculated at the 95% level for all primary outcomes.

Study Questions VS Analysis Plan

1. Can interactive educational sessions reduce **Community Periodontal Diseases Index** scores among 9th-grade students in Nablus City for two months?

1. Data Type and Variables

Dependent Variable: Community Periodontal Index for Treatment Needs (CPITN) **score** → Continuous quantitative variable

Independent Variable: Group type (Intervention vs. Control) → Binary categorical variable

Time Points: Pre-intervention (baseline)

Post-intervention (after two months) → true experimental design (pre-post measurements)

2. Statistical Design

Since there are two time points and two groups, the analysis includes:

A. Within-Group Analysis (Intervention group and control group):

Purpose: To assess whether there is a significant reduction in CPITN scores after the interactive educational sessions within the two groups themselves.

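### SAP Appendix A scores current smoking and ever having used a waterpipe in the wrong direction, so the smoking score can rank users above never-users; one brushing item is also misordered

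*SAP*

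**What the plan says.** The SAP lists smoking among its secondary objectives: "Secondary: To assess changes in oral hygiene practices, dietary habits, and smoking behaviours". Under question 3, questionnaire answers on oral hygiene, diet and smoking are recoded "to facilitate the computation of mean scores pre-and post-intervention", and answers reflecting preventive behaviour "were assigned the highest scores, while incorrect responses received the lowest scores". The smoking score is then compared between arms by independent t-test and tested before and after in the intervention arm only. It also enters an overall behaviour comparison.

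Appendix A, Section 4, gives the smoking codes. Three items follow the rule:

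- D.2: "D.2 - How frequently do you smoke cigarettes or use other tobacco products" runs from 1 (daily) to 4 (none).
- D.2.2: "D.2.2 - If you smoke cigarettes, how many cigarettes do you usually smoke per week" runs from 0 (26 and over) to 5 ("0-5cigarettes").
- D.4, current waterpipe frequency, runs from 1 (daily) to 4 (none).

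Two items do not. "D.1- Do you currently smoke (at least one cigarette" and "D.3 - Have you ever smoked a waterpipe (hookah" are both scored Yes = 2, No = 0.

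Appendix A, Section 2, scores brushing frequency (B1.1) as once a day 1, at least twice a day 2, sometimes 3. The worked example under question 3 instead gives 1, 2 and 3 to once, twice and three times a day.

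**The concern.** The items of one score should point the same way. Here D.1 and D.3 reward use and the other three penalise it, so a higher total does not consistently mean better behaviour. D.1 takes 2 points from a student who stops smoking, where a consistent code would add 2. D.3 asks about ever use, so it cannot improve on cessation in any case, and as printed it places ever-users above never-users.

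Two gaps in the specification affect how much this matters:

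- D.2.2 is addressed to smokers and has no separate non-smoker row. Its top band could include zero, so non-smokers either score 5 or skip the item.
- The SAP does not say whether items are summed or averaged. Its mention of mean scores may refer to group means.

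At stake is the meaning of a stated secondary outcome: a t-test on such a score cannot be read simply as improvement or deterioration. A larger sample does not cure that.

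**Working it through.** **Inputs.** All scores are the new scores printed in Appendix A. The documents report no smoking score to reproduce.

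| Item | Printed new scores | Against the SAP rule |
|---|---|---|
| D.1 current smoking | Yes 2, No 0 | opposite |
| D.2 frequency | daily 1, weekly 2, less than weekly 3, none 4 | follows |
| D.2.2 cigarettes per week | 26 and over 0, rising to 5 for 0-5 | follows |
| D.3 ever waterpipe | Yes 2, No 0 | opposite |
| D.4 waterpipe frequency | daily 1, weekly 2, less than weekly 3, none 4 | follows |

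Sum = D.1 + D.2 + D.2.2 + D.3 + D.4. Item mean = sum divided by the number of items answered.

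**Step 1: never-user against light user.** Take the reading kindest to the plan, in which non-smokers score 5 on D.2.2.

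- Never-user, printed: 0+4+5+0+4 = 13 (mean 13/5 = 2.6).
- Less-than-weekly user of both products, 0-5 cigarettes, printed: 2+3+5+2+3 = 15 (mean 3.0).
- D.1 and D.3 reversed: never-user 2+4+5+2+4 = 17; user 0+3+5+0+3 = 11.

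The user's gap goes from +2 to -6. If non-smokers skip D.2.2, the printed never-user has 0+4+0+4 = 8 (mean 8/4 = 2.0), still below the user's 15 (mean 3.0).

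**Step 2: quitting cigarettes.** Take a student who has never used a waterpipe (D.3 = 0, D.4 = 4). Before quitting, the sum is 2 + D.2 + D.2.2 + 0 + 4. Afterwards it is 13 with D.2.2 = 5, or 8 (mean 2.0) with D.2.2 skipped. Three D.2 levels by six D.2.2 bands give 18 patterns. Five pair less-than-weekly smoking with 6 or more cigarettes a week; removing them leaves 13. Each cell below counts patterns whose score is lower / unchanged / higher after quitting.

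| D.2.2 after quitting | Printed, 13 patterns | Printed, all 18 | D.1 and D.3 reversed, 13 patterns |
|---|---|---|---|
| scored 5, sum or mean | 1/1/11 | 1/2/15 | 0/0/13 |
| skipped, sum | 10/2/1 | 15/2/1 | 2/2/9 |
| skipped, item mean | 6/2/5 | 9/3/6 | 0/0/13 |

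With D.2.2 = 5, printed sums before quitting run from 2+1+0+0+4 = 7 to 2+3+5+0+4 = 14. The change on quitting therefore runs from 13-7 = +6 to 13-14 = -1. With D.1 reversed it runs from +10 to +3, always 4 more. The 2/2/9 cell shows that, on a sum, reversing D.1 and D.3 is not enough unless non-smokers also receive a D.2.2 score.

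**Step 3: waterpipe.** A past user who smokes nothing now scores 2 above a never-user on the sum: 15 against 13, or 10 against 8 if D.2.2 is skipped. For a non-smoker of cigarettes who starts waterpipe, D.3 adds 2 and D.4 falls. D.2 also falls if its reference to other tobacco products includes waterpipe.

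| New waterpipe use | D.2 ignores waterpipe | D.2 counts waterpipe |
|---|---|---|
| less than weekly | +2-1 = +1 | +2-1-1 = 0 |
| weekly | +2-2 = 0 | +2-2-2 = -2 |
| daily | +2-3 = -1 | +2-3-3 = -4 |

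**Step 4: B1.1.** The printed maximum over the 11 oral hygiene items is 1+3+3+3+3+3+3+1+3+3+4 = 30. A student who brushes at least twice a day can reach only 29. The new B1.1 scores equal the old codes, which suggests the item was never recoded.

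**The case against.** The case for treating this as minor has four parts.

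- **Scope.** Only secondary scores are affected, the same codes apply in both arms, and nothing in the documents shows that a conclusion would change. This is true and limits the claim. It does not make the score measure what the SAP says it measures.
- **Partial reversal.** With D.2.2 = 5, most quitting patterns still raise the total, and the heaviest user of both products (2+1+0+2+1 = 6) stays well below a never-user's 13. This stands: the score is distorted, not inverted, and the worse counts require non-smokers to skip D.2.2.
- **The pattern filter.** Daily smoking with 0-5 cigarettes a week could also be called inconsistent. It is possible, because D.2 covers other tobacco products. Dropping it leaves 12 patterns and printed counts of 1/1/10, 9/2/1 and 5/2/5, in the order of the table rows, so the direction is unchanged. In any case these are counts of answer patterns, not of students.
- **Applied coding unknown.** The SAP body and Appendix A already differ on brushing frequency, so the appendix may not match the syntax used. This stands, and it is why the remedy starts with a check. If the data were coded correctly, the appendix still misdescribes the outcome.

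**Conclusion.** The concern holds. As printed, D.1 and D.3 contradict the SAP's own scoring rule, and nothing elsewhere corrects them. On every reading of D.2.2 and of sum versus mean, a light user of both products outranks a never-user: by 2 points on the sum in the most favourable case, against 6 points below once D.1 and D.3 are reversed. Quitting cigarettes earns 4 points less than with D.1 reversed. B1.1 is separately misordered, but it only dilutes the oral hygiene score by a point and does not reverse that domain.

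The result rests on the printed codes having been used. The size of any bias in the arm difference cannot be calculated without smoking prevalence. CPITN, S-OHI, the diet domain score and the sample size are unaffected. No loss of non-smokers through complete-case analysis is claimed: the protocol (Instrument Development) says all participants completed the questionnaire, and the SAP describes missing data as minimal.

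**What to change.** 1. Check which codes were actually applied in SPSS.
2. Recode D.1 and D.3 to Yes = 0, No = 2. Leaving D.3 out of the change score, because an ever-use item cannot improve, is optional.
3. Score non-smokers 5 on D.2.2 and state that skipping this item is not missing data under the complete-case rule. On a sum this is needed as well as step 2; on an item mean the reversal alone restores the order in the patterns checked.
4. State whether the domain score is a sum or an item mean, and whether D.2 counts waterpipe.
5. Recode B1.1 so that brushing sometimes ranks below once a day, and once a day below at least twice a day. Align the example under question 3 with the appendix categories.
6. If the printed codes were used, recompute the smoking, oral hygiene and overall behaviour scores and rerun their t-tests.

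The cost is a check of the SPSS coding, a recode, a corrected appendix and two or three added sentences. If step 6 applies, the affected tests are rerun on existing data.
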